5.6 Premature Termination of the Trial

The clinical trial may be terminated prematurely at the request of Health Authorities or if new safety or efficacy information leads to an unfavorable benefit-risk judgment (e.g., due to evidence of inadequate drug exposure; occurrence of significant previously unknown adverse reactions or unexpectedly high intensity or incidence of known adverse reactions; or other unfavorable safety findings in this trial or the FIM trial or any other trial).

The Sponsor may discontinue the trial if it becomes unjustifiable for medical or ethical reasons, for poor enrollment making completion of the trial within an acceptable time frame unlikely, or because of discontinuation of clinical development of M3814.

Health Authorities and Independent Ethics Committees (IECs)/Institutional Review Boards (IRBs) will be informed about the discontinuation of the trial in accordance with applicable regulations.

5.7 Definition of End of Trial

The trial will end after the last subject in the Phase Ib part has completed the 1-year follow-up period or all subjects in the ancillary cPoP part of the trial have completed the 30-day follow up, whichever comes later.

6 Investigational Medicinal Product and Other Drugs Used in the Trial

The term “Investigational Medicinal Product” refers to an active substance or a placebo being tested or used as a reference therapy in a clinical trial, including products that have a marketing authorization but are formulated, packaged, or administered differently from the authorized form, used for an unauthorized indication, or used to gain further information about the authorized form.

In this trial, the term “Investigational Medicinal Product” refers to the investigational drug M3814, which is the only IMP used in this trial.

6.1 Description of the Investigational Medicinal Product

MSC2490484A, International Union of Pure and Applied Chemistry name (S)-[2-chloro-4-fluoro-5-(7-morpholin-4-yl-quinazolin-4-yl)-phenyl]-(6-methoxy-pyridazin-3-yl)-methanol, is supplied as 10 mg (size 4, ivory), 50 mg (size 0, ivory), and 100 mg (size 0, Swedish orange) hard gelatin capsules, as well as 50 mg (beige to yellow caplet) film-coated tablets for oral administration. Capsules consist of bulk drug substance filled into hard gelatin capsules of different size and/or color, depending on the dose strength. No further excipients are used. Hard gelatin capsule shells meet the supplier's (Capsugel®) standards and gelatin is of pharmacopoeial grade.

Film-coated tablets consist of a tablet core composed of extrudate (20% (w/w) drug substance/80% (w/w) copovidone solid dispersion) and other excipients [REDACTED]

[REDACTED]. All excipients used in the tablet formulation are of compendial grade. Supplier's certificates show that there is no transmissible spongiform encephalopathy risk.

MSC2490484 capsules and tablets are provided in [REDACTED] and should be stored [REDACTED]. The tablets should not be frozen.

6.2 Description of Concurrent Chemotherapy

Chemotherapy will be administered in combination with the IMP (M3814) in subjects enrolled in Arm B. The chemotherapy agent is cisplatin which is considered SoC for this indication. This chemotherapeutic agent is administered via intravenous (iv) infusion. Dose and dose regimen of cisplatin is to be applied in line with current medical guidelines (National Comprehensive Cancer Network, American College of Chest Physicians/ASCO, and European Society for Medical Oncology) with reference to the SoC for concurrent CRT with cisplatin in the treatment of subjects

with SCCHN. Two cisplatin dosing schedules are allowed, 100 mg/m² given twice or 40 mg/m² given weekly during the RT treatment. In addition to medical guidelines, dosing of cisplatin is to be performed in accordance with the product labeling and clinical site's specific policies/instructions. Cisplatin will not be supplied by the Sponsor. It will be used from commercially available sources and prepared in accordance with its product labeling.

6.3 Dosage and Administration

6.3.1 Phase Ia and Ib Parts

Subjects with locally advanced disease, as described in the Eligibility Criteria (Section 5.3), will be assigned to receive M3814 at a starting dose of 100 mg QD (Arm A) or 50 mg QD (Arm B) which will be given 1.5 hours (\pm 30 minutes) before each RT fraction for up to 10 fractions (Arm A) or for 33 to 35 fractions (Arm B).

In the Phase Ia part of the trial and for the first 3 subjects in Phase Ib (NSCLC expansion cohort), the dose of M3814 will be increased according to the dose escalation rules described in Section 5.1.1. No intrasubject dose escalation is permitted.

Subjects will take their assigned dose of M3814 QD with a full glass of water (approximately 240 mL/8 fluid ounces).

Subjects will be instructed as follows:

- On days with serial PK collections (Fraction Days 1 and 10), to fast 1.5 hours prior to dose administration and continue to fast for 4 hours postdose
- On all other Fraction Days, to fast 1.5 hours prior to dose administration and continue to fast for 1 hour postdose
- Take the prescribed dose of M3814 1.5 hours (\pm 30 minutes) before RT is started
- Swallow the capsules or tablets whole and not bite into the capsules, break or open them, or attempt to dissolve the contents in water prior to taking their assigned dose
- The doses on Fraction Days 1, 2, 6 and 10 should not be taken until the predose PK collection has been completed.

If a subject vomits after taking their dose of M3814, they should be given an antiemetic but no further dose will be given that day. Prophylactic antiemetics should then be given prior to subsequent doses of M3814. Any change from dosing schedule, dose interruptions, or dose reductions should be recorded in the eCRF.

The formal criteria for M3814, RT, and cisplatin dose modification in the trial are included in Table 13.

In general, each subject will stay on the M3814, RT and cisplatin (as applicable) dose level assigned in the trial unless treatment needs to be interrupted, modified or stopped. In all other situations, if the Investigator believes that a treatment-emergent adverse event (TEAE) is due to

cisplatin, the dose is to be modified according to the package insert/SmPC or local guidelines. A cisplatin dose delay of up to 1 week is permitted, in addition to the specific guidance provided below.

M3814 will be provided as tablet formulation of 50 mg for oral administration. Dosing schedule of the tablet formulation follows the description given for the capsule formulation above. The tablet formulation will be initially assessed in Phase Ia Arm A taking into account the available safety, tolerability and PK results from the capsule. Standard 3+3 dose escalation design criteria will apply. Comparison of single dose PK data between the tablet and the capsule will guide to define the tablet doses in Phase Ia Arm B and in the Phase Ib parts.

For subjects in Arm B receiving cisplatin:

- There will be no dose escalation of cisplatin above the protocol-specified dose. However, cisplatin dose re-escalation after an initial dose reduction, following the manufacturer's label, is permitted.
- Dose modifications for toxicity should be independently assessed prior to dose administration at each visit following institutional guidelines or [Table 13](#) in the absence of such guidelines.
- Prophylactic granulocyte-colony stimulating factor (G-CSF) may be implemented if neutropenia results in dose reduction or dose delay at prior doses, as suggested in the ASCO guidelines. Therapeutic use of hematopoietic colony-stimulating factors is permitted following ASCO guidelines.
- In the event a subject experiences neutropenia, and G-CSF is initiated, and neutropenia recovers within 48 hours after beginning treatment with G-CSF, G-CSF may be implemented in the management of neutropenia in this subject to avoid dose reductions or holding a dose.

Hemoglobin must be ≥ 10 g/dL at FD 1 and must be ≥ 9 g/dL for all subsequent doses. If hemoglobin is <9 g/dL then appropriate measures according to standard clinical practice must be taken prior to any further dose administration.

Table 13

Dose Modifications for M3814, Radiotherapy, and Cisplatin During the Trial

Toxicity	Dose Modifications		
	M3814 ^a	Radiotherapy ^b	Cisplatin (only for Arm B and in the absence of institutional guidance on cisplatin dose modifications)
Toxicities in Radiation Field Grade 4 
 Mucositis (mucosal inflammation) Radiation dermatitis 	Temporarily interrupt treatment. Resume treatment once severity resolves to Grade \leq 3.	Temporarily interrupt treatment. Resume treatment once severity resolves to Grade \leq 3.	Temporarily interrupt treatment. Resume treatment once severity resolves to Grade \leq 3.
Systemic Toxicities 
 Febrile neutropenia Grade 3 thrombocytopenia with medically concerning bleeding Hematologic Toxicities: Any Grade \geq 4 toxicity, excluding: 
 Grade 4 neutropenia lasting for \leq 5 days and not associated with fever Isolated Grade 4 lymphocytopenia without clinical correlate 	Temporarily interrupt treatment. Resume treatment (at the same dose) once severity resolves to Grade \leq 1 or Baseline. In case of a second recurrence at the same grade, permanently discontinue IMP.	No action to be taken.	Febrile neutropenia and Grade 3 thrombocytopenia with bleeding: permanent 25% dose reduction. If on the day of scheduled treatment with cisplatin ANC is $<$ 1500/mm 3 , hold treatment until ANC \geq 1500/mm 3 , then treat at 100% dose. If on the day of scheduled treatment with cisplatin the platelet count is $<$ 75,000/mm 3 , hold treatment until platelets are $>$ 75,000/mm 3 , then treat at 100% dose.
Systemic Toxicities 
 Nonhematologic Toxicities 
 Any Grade \geq 3 toxicity, excluding: 
 Diarrhea of Grade \geq 3 (\leq 3 days duration) following adequate and optimal therapy Nausea and vomiting of Grade \geq 3 (\leq 3 days duration) with adequate and optimal therapy Fatigue or headache of Grade 3 (\leq 7 days duration) following initiation of adequate supportive care Any other single laboratory values of Grade \geq 3 out of the normal range that have no clinical significance, and that resolve to Grade \leq 2 with adequate measures within 7 days 	Temporarily interrupt treatment. Resume treatment (at the same dose) once severity resolves to Grade \leq 1 or Baseline. In case of a second recurrence at the same grade, permanently discontinue IMP. In case of Grade \geq 3 liver enzyme values, the subject must be monitored at least every 4 days until recovery to Grade \leq 2.	No action to be taken.	Institutional guidelines.

- Evidence of study treatment-related hepatocellular injury for more than 3 days, such as > 5-fold elevations above the ULN of ALT or AST (CTCAE Grade 3 or 4) with or without elevation of serum total bilirubin to > 2 x ULN, without initial findings of cholestasis (elevated serum a kaline phosphatase) or other apparent clinical causality.

AE = adverse event; ALT = alanine aminotransferase; ANC = absolute neutrophil count; AST = aspartate aminotransferase; CTCAE = common terminology criteria for adverse events; IMP = investigational medicinal product; RT = radiotherapy; ULN = upper limit of normal.

Note: Severity of AEs will be graded using the CTCAE (v4.03) toxicity grades.

^a As all treatments with M3814 will be given in combination with RT, an interruption in the administration of RT would lead to an interruption in treatment with M3814.

^b A maximum RT delay of up to and including 7 days in total is allowed within the complete treatment period. If RT and M3814 treatment have to be delayed by more than 7 days, the subject must be discontinued from M3814.

As all treatments with M3814 will be given in combination with RT, an interruption in the administration of RT would lead to an interruption in treatment with IMP. See Section 6.6.3.1 for details on handling RT treatment delays.

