The ancillary cPoP part of the trial will initially be conducted with the capsule formulation; however, additional cohorts of M3814 (CC1 formulation) may be introduced. The starting dose and subsequent dose levels of M3814 (CC1 formulation) will be defined by the SMC based on PK and safety data generated in ongoing clinical studies evaluating the safety, tolerability, PK, and PD of M3814 (CC1 formulation).

CCI

CCI

tablet formulation of M3814:

M3814 will be provided as CCI tablet formulation of 50 mg, for oral administration. Dosing schedule of the tablet formulation follows the description given for the capsule formulation above. The tablet formulation will be initially assessed in Phase Ia Arm A taking into account the available safety, tolerability and PK results from the capsule. Standard 3+3 dose escalation design criteria will apply. Evaluation of single dose PK data after administration of the tablet and the capsule in the same subject will support the selection of tablet doses in Phase Ia Arm B, the Phase Ib parts and in the additional cohorts of M3814 in the ancillary cPoP part of the trial.

Concurrent cisplatin - Dose/mode of administration/dosing schedule:

Concurrent cisplatin will be administered in combination with the IMP in subjects with SCCHN included in Phase Ia Arm B and the SCCHN expansion cohort in Phase Ib. The dose and dose regimen of cisplatin is to be applied in line with current medical guidelines (NCCN, ACCP/ASCO, and ESMO) with reference to the Standard of Care (SoC) for concurrent CRT with cisplatin in the treatment of subjects with SCCHN. Cisplatin will be given twice at a dose of 100 mg/m² or weekly at a dose of 40 mg/m².

Planned trial and treatment duration per subject:

Treatment duration is expected to be approximately 2 weeks (Arm A) or 7 weeks (Arm B) for the Phase Ia part, 6-7 weeks for the Phase Ib part, and 2 days for the ancillary cPoP part.

Statistical methods:

In the Phase Ia part, for each arm (A and B) the sample size will depend on the number of DLTs observed at the different dose levels and the number of tested or expanded dose levels for M3814. Subjects will be enrolled in cohorts of 3 subjects.

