The Phase Ib part consists of one expansion cohort per arm from the Phase Ia part. For Arm A, the expansion cohort will explore the activity of M3814 combined with RT in treatment-naïve subjects with Stage III A/B NSCLC. The cohort will enroll up to 27 evaluable subjects including the safety run-in part, bringing the anticipated maximum sample size for the Phase Ia/Ib parts to 75 subjects for Arm A. A sample size of 27 evaluable subjects will enable the lower limit of a 2-sided 95% confidence interval (CI) for the response rate to extend no further than an absolute 20% from the expected proportion of 50%, thereby ensuring the lower limit is no less than the historical control of 30% in treatment-naïve subjects with Stage III A/B NSCLC.

For Arm B, the anticipated sample size in the escalation part is 30 participants (together for tablet and capsule). The expansion cohort will explore the safety, tolerability and efficacy of M3814 combined with CRT (with cisplatin) in treatment-naïve subjects with SCCHN. A sample size of up to 27 evaluable subjects will be enrolled to confirm safety and tolerability of the combination. Together, this brings the anticipated sample size for the Phase Ia/Ib parts to 57 subjects for Arm B.

For the ancillary cPoP part of the trial conducted in parallel with the Phase Ia part, a fixed number of 3 subjects will be enrolled at the two lower fixed dose levels and 5 subjects will be enrolled at the RP2D. Assuming a correlation between the fold induction of the marker and the dose is 0.69, the power of detecting a linear relationship is 80% with an alpha-level of 5% (2-sided). In case the PD results don't allow detection of sufficient modulation of target engagement i.e., a clear dose/effect relationship between levels in pre- and on treatment tumor biopsies, additional dose

level(s) could be explored upon SMC decision according to the findings during the escalation phase in Phase Ia. Approximately 12 additional subjects may be enrolled in the ancillary cPoP part of the trial using M3814 CCI formulation, thus leading to a maximum sample size in the ancillary cPoP part of 23.

The anticipated total number of evaluable subjects to be included in the three parts of the trial with additional cohorts in the ancillary cPoP part of the trial is therefore 155. Considering a drop-out rate of 10% for subjects not evaluable for DLT assessment in Phase Ia, approximately 165 subjects need to be enrolled in the trial.

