- y. Subjects treated in the tablet testing cohorts of Phase Ia Arm A will receive the tablet on FD 1-5 and FD 7-10 and a respective single dose strength of the capsule formulation on FD 6.

- z. If FD6 is NOT on a Monday then it must be scheduled to take place on the Monday closest to FD6 as wash-out over the weekend is required.
- aa. PTD 210 and 312 will consist of phone calls to evaluate long term RT toxicity. No other assessments will be performed at these visits.

Table 3 Schedule of Assessments – First 3 Subjects in Phase Ib (Arm A; NSCLC Cohort)

Trial Periods	Screening	DLT Evaluation Period						DLT Period/Short-term Safety FU	Mid-term Safety FU	Long-term Safety FU/ EOT ^a	Survival FU
		Treatment Period (M3814 + RT)									
Trial Days	Day -21 to Day -1	FD 1 to FD 33						PTD 1 to 37	PTD 1 to 90	PTD 31 to 365	-
M3814 RT 2 Gy x 33 (5 F/W) ^b		X X									
Visit Days	-21 to -1	FD 1	FD 2	FD 6	FD 10 ^c	FD 16, 21, 26 and 33/ETT ^d	PTD 8, 15, 22, 37 ^e	PTD 84	PTD 42, 126, 168, 180, 210 ^x , 270, 312 ^x , and 365	-	-
Visit Window (days)	-	-	-	-	-	-	±2	±7	±7	-	-
Signed informed consent	X										
Inclusion/exclusion criteria	X	X									
Demography	X										
Medical history	X										
Serum β-HCG pregnancy test (if applicable)	X						PTD 22 only				
Infection screen (hepatitis B and C), optional HIV test ^f	X										
Vital signs ^g	X ^h	X		X	X	X	X	X	X		
Physical examination	X	X		X	X	X	X	X	X ⁱ		
Clinical examination of bleeding	X	X		X	X	X	X				

Trial Periods	Screening	DLT Evaluation Period						DLT Period/Short-term Safety FU	Mid-term Safety FU	Long-term Safety FU/ EOT ^a	Survival FU
		Treatment Period (M3814 + RT)									
Trial Days	Day -21 to Day -1	FD 1 to FD 33						PTD 1 to 37	PTD 1 to 90	PTD 31 to 365	-
M3814 RT 2 Gy x 33 (5 F/W) ^b		X X									
Visit Days	-21 to -1	FD 1	FD 2	FD 6	FD 10 ^c	FD 16, 21, 26 and 33/ETT ^d	PTD 8, 15, 22, 37 ^e	PTD 84	PTD 42, 126, 168, 180, 210 ^x , 270, 312 ^x , and 365		-
Visit Window (days)	-	-	-	-	-	-	±2	±7	±7		-
Esophageal endoscopy (if relevant)	X										
Evaluation of all tissues in RT area				X	X	X	X	X	X		
ECOG PS	X				X	FD 33 only	X	X	X		
Adverse event assessment	X	X		X	X	X	X	X ^f	X ^f		
Concomitant medication	X	X		X	X	X	X				
Hematology ^k	X	X		X	X	X	X				
Serum chemistry and coagulation ^l	X	X		X	X	X	X				
Urinalysis (dipstick) ^m	X				X	FD 16 and 33 only	X				
12-lead ECG (including QTcF) ⁿ	X	X ^o			X ^p						
Tumor assessment (RECIST) ^{q, r}	X							X	X		
PK blood samples ^s		X	X ^t	X	X						

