Table 9 Pharmacokinetic and **CCI** Sampling Schedule of M3814 during Phase Ia, Phase Ib, and the Ancillary cPoP Part of the Trial

	Time points Volume of blood required per time point ^a	Phase Ia		Phase Ib ^b		Ancillary cPoP	
		PK ^c 2 mL	CCI	PK ^c 2 mL	CCI	PK ^c 2 mL	CCI
FD 1	Predose	X		X			
	H 0.5	X		X			
	H 1.0	X					
RT	1.5 hours (± 30 minutes) after dosing	3 Gy x 10; 5 2 Gy x 33-35;		2 Gy x 33; 5 2 Gy x 33-35; 5		10-25	
	H 2.0	X		X			
	H 4.0	X		X			
	H 6.0	X		X			
FD 2	Predose ^d	X				X	
	H 0.5					X	
	H 1.0					X	
RT	1.5 hours (± 30 minutes) after dosing	3 Gy x 10; 5 2 Gy x 33-35;		2 Gy x 33; 5 2 Gy x 33-35; 5		10-25	
	H 2.0					X	
	H 4.0					X	
FD 6	Predose ^d	X					
	H 0.5 ^g	X					
	H 1.0 ^g	X					
RT	1.5 hours (± 30 minutes) after dosing	3 Gy x 10; 5 2 Gy x 33-35;		2 Gy x 33; 5 2 Gy x 33-35; 5			
	H 2.0 ^g	X					
	H 4.0 ^g	X					
	H 6.0 ^g	X					
FD 7^g	Predose ^d	X					
FD 10^f	Predose ^d	X		X			
	H 0.5	X		X			
	H 1.0	X					
RT	1.5 hours (± 30 minutes) after dosing	3 Gy x 10; 5 2 Gy x 33-35;		2 Gy x 33; 5 2 Gy x 33-35; 5			
	H 2.0	X		X			
	H 4.0	X		X			

cPoP = clinical proof-of-principle; FD = fraction day; F/W = fraction per week; Gy = Gray; NSCLC = non-small cell lung cancer; **CCI** ; PK = pharmacokinetic; RT = radiotherapy; SCCHN = squamous cell carcinoma head and neck; SMC = Safety Monitoring Committee.

[figure not shown]
- a Pharmacokinetic sampling should be performed within \pm 15 minutes of the first 30 minute postdose sample collections, and within \pm 30 minutes for subsequent sampling at each sampling day. The predose sample should be taken within 1 hour before dosing at each sampling day.
- b PK and CCI sampling for the first 3 subjects in Phase Ib (NSCLC expansion cohort) will follow the same schedule as for Phase Ia, as shown in this table.

CCI

- d For the purpose of PK parameter calculations, the predose value will also serve as an estimate for the 24-hour postdose concentrations of the previous FD.
- e The blood sample closest in time to the biopsy should be collected as close as possible to the time of the biopsy.
- f If FD 10 is on a Friday, PK and CCI sampling must be done on FD 9.
- g Only for patients treated in the tablet testing cohorts in Phase Ia Arm A.

CCI

2

Sponsor, Investigators and Trial Administrative Structure

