5.1.2 Tablet Formulation Introduction, Evaluation, and SMC Decision Making

In addition to the capsule formulation used in this and previous studies, a tablet formulation has been developed. Owing to its formulation characteristics, dissolution of the drug substance may be enhanced in the tablet compared to the capsule formulation. CCI

Physiology-based (GastroPlus) modeling of the human absorption which is predicted to be > 90% at daily doses up to 400 mg, and > 50% at daily doses up to 1000 mg. To take a conservative approach, exposure increases of 2-fold relative to the capsule formulation is assumed.

Currently doses and exposures of up to 200 mg QD of the capsule formulation in combination with RT are considered safe and well tolerated by the SMC. Dose escalation in the current trial is ongoing and the dose of 300 mg is currently being tested. Considering the scenario of an exposure increase of 2-fold of the tablet relative to the capsule formulation a starting dose of 100 mg QD has been selected.

Introduction of the tablet in the Phase Ia part of Arm A

The tablet formulation will be introduced in Phase Ia Arm A of this trial taking into account the available clinical experience and exposure reached after administration of the capsule formulation of M3814 in combination with RT. Subjects will receive the tablet formulation at a starting dose of 100 mg QD on trial days FD 1-5 and FD 7-10. On trial day FD 6, the current capsule formulation will be given as a single dose of 100 mg to allow an intra-individual cross over comparison of single dose PK between the tablet and the capsule formulation. The administration of M3814 formulations will take place 1.5 hours (\pm 30 minutes) before the start of RT. In subsequent dose levels tablet and capsule formulations will always be given using the same dose.

After an initial cohort of 3 patients has been treated at the initial tablet dose of 100 mg, the SMC will decide to treat further patients at this tablet dose with the same dose, or to test optional dose levels (either decreases or increases of dose, the nominal dose will be the same as for the tablets). To decide on the doses to be tested, the SMC will review all available safety, tolerability and PK data, e.g., t_{max} , C_{max} , AUC_{0-24} after single doses of the capsule (FD6) and the tablet (FD1) formulations. The goal is to achieve exposures close to those achieved at the RP2D established for the capsule.

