AUC ₀₋₁₂ /Dose	The Dose-normalized AUC from time zero to 12 hours postdose. Normalized using the actual dose, using the formula AUC ₀₋₁₂ /Dose.
t _{max}	Time to reach the maximum observed concentration C _{max}
t _{last}	The last sampling time at which the concentration is at or above the lower limit of quantification (LLOQ).
R _{acc(Cmax)}	Accumulation ratio for C _{max} , calculated as C _{max} CCI C _{max,FD1} (all dose groups)
F _{rel(Cmax)}	Relative bioavailability for C _{max} of tablet compared to capsule formulation C _{max,FD1} /C _{max} C (tablet testing group only)
R _{acc(AUC0-4)}	Accumulation ratio for AUC ₀₋₄ calculated as AUC ₀₋₄ CCI AUC _{0-4,FD1} (all dose groups)
F _{rel(AUC0-4)}	Relative bioavailability for AUC ₀₋₄ of tablet compared to capsule formulation AUC _{0-4,FD1} /AUC ₀₋₄ C (tablet testing group only)
R _{acc(AUC0-6)}	Accumulation ratio for AUC ₀₋₆ calculated as AUC ₀₋₆ CCI AUC _{0-6,FD1} (all dose groups)
R _{acc(AUC0-12)}	Accumulation ratio for AUC ₀₋₁₂ calculated as AUC ₀₋₁₂ CCI AUC _{0-12,FD1} (all dose groups)
R _{acc(AUC0-24)}	Accumulation ratio for AUC ₀₋₂₄ calculated as AUC ₀₋₂₄ CCI AUC _{0-24,FD1} (all dose groups)
F _{rel(AUC0-24)}	Relative bioavailability for AUC ₀₋₂₄ of tablet compared to capsule formulation AUC _{0-24,FD1} / AUC ₀₋₂₄ C (tablet testing group only)
AUC ₀₋₂₄	Area under the concentration-time curve (AUC) from time zero to time 24 hours. AUC _{0-24h} will be calculated after the first dose on Fraction Day 1 and after dosing on Fraction Day 6 (in tablet testing group only) and Fraction Day 10. AUC ₀₋₂₄ will be based on the estimated concentration at 24 hours, and not the concentration at the actual observation time. For FD1 and CCI in case no regression is available and a sample has been collected at 24 hours within the protocol-defined collection window (23.5 to 24.5 hours), actual time may be used. For CCI where available, the pre-dose concentration will be duplicated and used as the 24 hour concentration to allow AUC ₀₋₂₄ to be calculated (assuming steady state after multiple dosing).
AUC ₀₋₂₄ /Dose	The Dose-normalized AUC from time zero to 24 hours. Normalized using the actual dose, using the formula AUC ₀₋₂₄ /Dose.

$C_{av,0-24}$	Average concentration from time zero to 24 hours. Formula: $AUC_{0-24}/24$.

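### In the tablet cohorts, the protocol applies a 4-hour postdose fast to the tablet PK profile and a 1-hour fast to the capsule profile, so the within-subject ratio mixes formulation with meal timing

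*Protocol*

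**What the plan says.** **Fasting rule.** Protocol section 6.3.1 sets a 4-hour postdose fast through this instruction: "On days with serial PK collections (Fraction Days 1 and 10), to fast 1.5 hours prior to dose administration". The next instruction covers the rest: "On all other Fraction Days, to fast 1.5 hours prior to dose administration and continue to fast for 1 hour postdose". The predose fast is 1.5 hours in both cases. The tablet text in the same section adds no fasting rule and refers back to the capsule description.

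**Sampling and dosing in the tablet cohorts.** Table 2 gives the tablet on FD1-5 and FD7-10 and a single capsule dose on FD6. If FD6 is not a Monday, footnote z says "it must be scheduled to take place on the Monday closest to FD6 as wash-out over the weekend is required". Table 9 schedules FD6 samples at 0.5, 1, 2, 4 and 6 hours after the predose sample. Footnote g restricts the postdose ones: "Only for patients treated in the tablet testing cohorts in Phase Ia Arm A".

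**Purpose and use.** Section 5.1.2 gives the capsule dose "to allow an intra-individual cross over comparison of single dose PK between the tablet and the capsule formulation", and names capsule FD6 and tablet FD1 as the profiles the SMC reviews. SAP section 16.1 defines relative bioavailability "of tablet compared to capsule formulation" for Cmax, AUC0-4 and AUC0-24, with FD1 in the numerator. The denominator day is blacked out there, but section 5.1.2 identifies it. The Synopsis says that single-dose data on both formulations "in the same subject will support the selection of tablet doses in Phase Ia Arm B", the Phase Ib parts and the additional cPoP cohorts.

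**The concern.** A within-subject comparison of two formulations assumes that other conditions are the same on both occasions. Here the written rules allow food between 1 and 4 hours postdose on the capsule day and forbid it on the tablet day. The tablet always comes first, so the fasting rule is fully confounded with formulation. Neither pairing within subjects nor adding subjects removes the difference.

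The protocol itself gives reasons to care about this window. It asks for a longer fast on its serial PK days than on ordinary days. Section 6.6.2 says that solubility depends on pH and restricts antacids until 2 hours after dosing. The capsule contains drug substance without excipients, while the tablet is a solid dispersion (section 6.1), so the two need not respond to food in the same way.

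At stake is a ratio that feeds tablet dose selection in Arm B and Phase Ib, where treatment has curative intent.

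A smaller, separate point concerns the multiple-dose profile. When FD10 is a Friday it moves to FD9 (section 7.5.2.1), which is also off the 4-hour list. Accumulation ratios against FD1 could then mix fasting conditions. FD9 does not enter the tablet/capsule ratio.

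**Working it through.** The plan states no figure of its own to reproduce. The check compares the rules and works through the calendar.

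**1. Which fast applies to which profile**

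| | Tablet profile | Capsule profile |
|---|---|---|
| Day | FD1 | FD6 or nearest Monday |
| Predose fast (6.3.1) | 1.5 h | 1.5 h |
| Postdose fast (6.3.1) | 4 h | 1 h |
| Place in F_rel | numerator | denominator |

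**2. Can the capsule day ever be a 4-hour day?** Inputs: 5 fractions per week, no interruption, nearest Monday counted in calendar days.

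| Start | FD6 falls on | Capsule day | FD10 falls on |
|---|---|---|---|
| Mon | Mon | FD6 | Fri, so profile on FD9 |
| Tue | Tue | FD5 (1 day earlier) | Mon |
| Wed | Wed | FD4 (2 days earlier) | Tue |
| Thu | Thu | FD3 (3 days earlier; next Monday is 4 days later) | Wed |
| Fri | Fri | FD7 (3 days later; previous Monday is 4 days earlier) | Thu |

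The capsule day is FD1 or FD10 in 0 of 5 cases. The multiple-dose profile moves off the 4-hour list in 1 of 5 (Monday start).

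**3. How much of the profile is under different rules**

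- Span: 4 h − 1 h = 3 h.
- Share of the AUC0-4 window: 3/4 = 75%.
- Share of the AUC0-24 window: 3/24 = 12.5%.

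The 0.5 h and 1 h samples are under the same rule on both days, and the 2 h sample is not. These are shares of time under different instructions, not estimates of bias.

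**4. How many subjects**

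- The Synopsis (Statistical methods) allows 27 subjects in Phase Ib Arm A, "bringing the anticipated maximum sample size for the Phase Ia/Ib parts to 75 subjects for Arm A". Up to 30 are anticipated for capsule escalation.
- Implied tablet subjects: 75 − 27 − 30 = 18.
- Cross-check from the Synopsis Phase Ia total of about 78, with 30 in Arm B: 78 − 30 − 30 = 18.

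**5. What unequal fasting could do (illustration only)**

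Let f be the multiplicative effect on capsule exposure of eating between 1 and 4 hours. Then observed F_rel = true F_rel / f. Take a true ratio of 2.0, which is the conservative assumption in section 5.1.2, and an assumed f of 0.80 to 1.25. The range for f is not from the documents.

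- f = 0.80: 2.0/0.80 = 2.50
- f = 1.00: 2.0/1.00 = 2.00
- f = 1.25: 2.0/1.25 = 1.60

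With the same fast on both days the fasting rule no longer differs, and f = 1 by design.

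**The case against.** **The wording is ambiguous.** The governing phrase in section 6.3.1 is about days with serial PK sampling, and in the tablet cohorts FD6 is such a day. A site could reasonably apply 4 hours. The section's day lists are also incomplete elsewhere: its predose-sample instruction omits FD7, which Table 9 requires in the tablet cohorts. This is fair as to intent. But the parenthesis names two days and the next instruction assigns all the others to 1 hour, so a site following the text would use 1 hour.

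**The practical effect may be small.** Radiotherapy is given 1 to 2 hours after dosing, which limits eating before the 2-hour sample. After 4 hours the rule is the same on both days. Food is permitted, not required. All of this stands, and it limits the weight of the point. Even with radiotherapy at 2 hours, about 2 hours remain, less the session time, in which food is allowed.

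**Other data protect dose selection.** The tablet target is the exposure at the capsule RP2D. The capsule cohorts' FD1 and FD10 profiles were under the same 4-hour rule as tablet FD1, so that comparison is matched on fasting. The SMC also weighs safety and other PK data, Arm B remains under overdose control, and section 5.1.2 starts the NSCLC run-in one dose level lower. These are real safeguards. The matched comparison, however, is between subjects and does not repair the within-subject ratio that was planned.

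**FD9.** It is natural to read the FD10 conditions as moving with the profile. That is probably the intention, and this part is secondary.

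**Conclusion.** The concern holds. As written, the fasting rule differs between the tablet and capsule profiles for every start weekday and every tablet-cohort subject, up to about 18, always in the same direction. The difference covers 1 to 4 hours postdose. F_rel for Cmax, AUC0-4 and AUC0-24 may therefore reflect meal timing as well as formulation.

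The mismatch in the instructions is certain on the visible text. The bias is only possible. It depends on whether subjects ate in that window and on a food effect that the documents do not report, so its size and direction are unknown. The calendar result assumes no treatment interruption. The point deserves correction because the comparison guides tablet doses and the remedy is cheap, not because a wrong dose has been shown to follow.

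**What to change.** **Protocol section 6.3.1 and site instructions.** Apply the 4-hour postdose fast to every full-profile day: FD1; in the tablet cohorts the capsule day, whether FD6 or the Monday that replaces it; and FD10, or FD9 when the profile is moved there. If that was always the intention, the sentence simply makes it explicit.

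**SAP section 16.1.** Add a footnote to any F_rel or accumulation ratio already obtained under unequal fasting rules. Neither document describes recording meal times, so the footnote has to follow the rule in force for that day rather than what each subject actually did. It is still useful if tablet-cohort dosing is complete. The main correction does not depend on it.

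**Cost.** One sentence in the protocol and site instructions and one footnote in the SAP. Subjects fast about 3 more hours on the capsule day and, for Monday starts, on FD9 in place of FD10. No additional blood samples are needed.
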